### 6.3 Data Analysis

Data validation and quality control will first be performed through a descriptive analysis, expressing frequencies and extreme values for all recorded variables. Any errors detected will be corrected through a search for and recovery of missing data and an analysis of inconsistencies. Subsequently, a description of the sample will be provided, expressing the frequency distribution of the qualitative variables, and the arithmetic mean, median, and standard deviation, as well as maximum and minimum values for the quantitative variables.

The main analysis will consist of estimating the frequency and/or mean of post-treatment changes (reduction/increase). A paired data analysis of the changes will also be performed. A mixed-effects analysis (linear link GLM) will be performed for continuous variables. This same analysis will be performed for other dichotomous efficacy variables (improvement or lack thereof in each parameter) using logistic link GLM models. In addition, for the comparative analysis from time 0 to 6 months, parametric and nonparametric comparison tests (Student's t-test, chi-square, Wilcoxon test) and linear regressions will be applied to observe the influence between variables, taking into account the follow-up time. Family units will be phenotyped based on their variables by creating clusters using the k-means algorithm.

In all analyses, a type I error or  $\alpha$  of 5% will be established, with statistical significance when p values are less than 0.05, and a type  $\beta$  error of 20% (statistical power of 80%). Statistical analyses will be performed using the R Core Team statistical package (2023) v. 4.3.

#### **6.4 Sample Size**

The sample size was calculated based on the results of a previous study published by our group on the dietary pattern of adult patients with T1D compared to subjects without diabetes in Spain (6). This is the most informative method available, and we assume that the adults in our study will have a similar pattern. We considered the mean and standard deviation of a group of adult individuals with T1D for adherence to the Mediterranean Diet, calculated with aMED. With a statistical power of 80% and an alpha error of 5%, it was calculated that a total of 26 newly diagnosed patients (one family unit) would be necessary to detect a minimum difference of 1 point on the aMED, performing the mean comparison test for two paired samples (pre-post analysis). As a contingency, recruiting 16 family units would also guarantee a statistical power of 80% and an alpha error of 5% to detect a minimum difference of 5 points in the aHEI index. The latter is also based on our own study in the T1D population. The family unit can be composed of both or just one parent, as long as they are responsible for most of the family meals. In the case of patients with shared custody, if the patient spends 40% or more of their time with one family, that family will be counted as a family unit.

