## 1. RESUME

|                                  |  |
|----------------------------------|--|
| Promoter identification   | Institut de Recerca Sant Pau (IR SANT PAU)
[name],
[name]
[contact]  |
| Study title               | Dietary changes in adults in the family unit in newly diagnosed pediatric cases of type 1 diabetes: impact of educational actions on routine practice  |
| Code                      | IIBSP-DDM-2023-166   |
| Protocol version and date | Version: 2.0 Approval date: 19/02/2024   |
| Coordinator investigator  | [name], Endocrinology and Nutrition service
Hospital de la Santa Creu i Sant Pau
[name]
[name]
[contact]
e-mail: [contact]  |
| Principal investigator    | [name], IR SANT PAU
e-mail: [contact]   |
| Collaborator researchers  | [name]
[name]
[name]
[name]
[name]
[name]
[name]
[name]
[name]
[name]
[name]
[name]
[name]
[name]           |
| Centros participantes     | Hospital de la Santa Creu i Sant Pau, Barcelona
Hospital Universitari Arnau de Vilanova, Lleida
Hospital Sant Joan de Déu, Esplugues de Llobregat  |
| Reference ethics comitee  | CEI Sant Pau   |
| Principal Aim             | To characterize dietary patterns in the family (parents or guardians) of people newly diagnosed with type 1 diabetes mellitus at the time of diagnosis, and to evaluate their evolution and the effect on health indicators after one year of evolution. |
| Design                    | Observational study on a prospective cohort  |

|  |  |
|--|--|
| Disease of study                              | Type 1 Diabetes mellitus   |
| Methods                                       | Recruitment of 26 family units of newly diagnosed patients with T1D (pre-screened upon hospital admission).
Inclusion visit (within the first week of diagnosis).
Follow-up visits at 6 months.
Final visit at 12 months. |
| Study population and total number of subjects | 26 family units (parents or guardians) of newly diagnosed T1D patients.  |

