## 5. METHODS

### 5.1 Study Design

This study will be a prospective, multicenter, observational study. The study will be conducted within the Pediatrics Department of the Hospital de la Santa Creu i de Sant Pau (HSCSP) (Barcelona) and the Hospital Universitari Arnau de Vilanova (HUAV) (Lleida). This study will be launched at the participating centers once a favorable opinion has been obtained from the Research Ethics Committee, and in accordance with the legislative requirements for this type of observational study.

The study design includes an initial visit that will coincide with the patient's inclusion in the study. Prior to the inclusion visit, a pre-screening period is planned. During this period, the potential candidate and their family will be invited, all study procedures will be explained and clarified, the selection criteria will be verified, and the inclusion visit will be scheduled. A follow-up visit will be conducted at 6 months throughout the study. A final visit will be conducted 12 months after enrollment (with a 1-month window).

Adult subjects from 26 households of patients recently diagnosed with T1D are planned to be included.

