#### *5.5.3 Withdrawal criteria:*

All participants have the right to withdraw from the study at any time, withdrawing their consent, without having to justify this decision and without any detriment to their clinical follow-up. Participants may also revoke the use of their data in the analysis, without justifying their decision, and without incurring any liability or harm.

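### Section 6.4 calls 26 units necessary for 80% power on aMED and the study enrols exactly 26, with no stated allowance for loss over 12 months (minor)

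*Protocol*

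**What the plan says.** Protocol section 6.4 gives the required number: "a total of 26 newly diagnosed patients (one family unit) would be necessary to detect a minimum difference of 1 point on the aMED". The test is a paired comparison of means, with 80% power and 5% alpha. The section takes the SD from the group's earlier study of adults with T1D but does not print it.

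The planned enrolment is the same number. Section 1 has "Recruitment of 26 family units of newly diagnosed patients with T1D", and section 5.1 has "Adult subjects from 26 households of patients recently diagnosed with T1D are planned to be included".

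The primary objective (section 4.2) is change at one year, so a complete pair needs the 12-month visit. Section 5.5.3 lets participants withdraw at any time, and "Participants may also revoke the use of their data in the analysis". No section gives a loss rate, an inflation of the sample or a replacement rule. Section 6.5 lists the small sample as a limitation but does not mention loss.

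The only contingency in section 6.4 is on another index: "As a contingency, recruiting 16 family units would also guarantee a statistical power of 80"%, for a 5-point difference in aHEI. The section adds that "The family unit can be composed of both or just one parent".

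**The concern.** If 26 complete pairs are needed and 26 units are enrolled, the stated 80% holds only if almost every unit gives a usable 12-month pair. Some loss is likely in a one-year follow-up of parents dealing with a new diagnosis. The power figure in section 6.4 would then be higher than the study can be expected to deliver on the index used for sizing. A null aMED result would be read against a power that was not available.

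**Working it through.** **Inputs.** From section 6.4: difference 1 aMED point, alpha 5%, power 80%, paired test, n = 26. Not given: SD of within-person change, sidedness, expected loss. Assumed here: two-sided test, one pair per unit, no hidden allowance in 26, and illustrative random loss of 5 to 20%.

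**Step 1: the plan's own figure.** Without an SD, 26 cannot be reproduced forwards, so I solved backwards. For n pairs, the t statistic has n − 1 degrees of freedom and noncentrality (1/SD) × √n. Power is the probability that it exceeds the two-sided 5% critical value in absolute size. Power reaches 80% with 25 pairs at SD 1.712 and with 26 pairs at SD 1.749. So 26 is the smallest sufficient number for an SD of change between 1.712 and 1.749. The figure is attainable, but it cannot be verified.

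**Step 2: power with fewer complete pairs.**

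| Complete pairs | SD 1.712 | SD 1.749 |
|---|---|---|
| 26 | 81.6% | 80.0% |
| 25 | 80.0% | 78.3% |
| 24 | 78.2% | 76.5% |
| 23 | 76.3% | 74.6% |
| 22 | 74.3% | 72.5% |
| 21 | 72.1% | 70.3% |
| 20 | 69.8% | 67.9% |

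**Step 3: expected power under random loss.** The number of complete pairs is taken as binomial (26, 1 − loss), and power is averaged over it.

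| Assumed loss | SD 1.712 | SD 1.749 |
|---|---|---|
| 5% | 79.4% | 77.7% |
| 10% | 76.9% | 75.2% |
| 15% | 74.3% | 72.5% |
| 20% | 71.3% | 69.5% |

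The difference detectable with 80% power rises from 1 point to 1.02–1.05 with 24 pairs and 1.13–1.16 with 20.

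**Step 4: does the contingency help?** It does not help aMED: 16 pairs give 57.1 to 58.9%. For aHEI (5 points, 16 units) the same back-solution gives an SD of 6.43 to 6.67. Power for aHEI is then 95.6 to 96.8% with 26 pairs and 88.8 to 91.0% with 20, so there is room for loss on that index.

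**Step 5: sensitivity to the assumptions.**
- One-sided t-test: the implied SD is 1.95 to 1.99. Power is 77.0 to 78.5% with 24 pairs and 69.7 to 71.3% with 20, nearly the same fall.
- 26 already includes loss: 24/0.95 = 25.3, 23/0.90 = 25.6 and 22/0.85 = 25.9 all round up to 26. The implied SDs are 1.64–1.68, 1.60–1.64 and 1.56–1.60, and 80% then survives a loss of 5, 10 or 15% respectively.
- Other SDs of change: 1.5 gives 90.4% with 26 pairs and 80.7% with 20; 2.0 gives 68.8% and 56.5%.

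**The case against.** The strongest reply is that no error has been shown. The SD comes from the group's own published study, 26 may already include loss, and even at 10% loss expected power falls only to about 75 to 77%. Section 6.5 already admits a small, feasibility-driven sample. This stands, and it is why the point is minor. It does not remove the point: section 6.4 words 26 as what is needed, and sections 1 and 5.1 enrol that number. The missing SD is by itself only missing detail.

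Other features may soften the effect. A unit can include two parents. Section 5.4 admits both households when the child's time is shared equally, so some index patients may give more than one pair. Visits follow routine check-ups (section 5.3), and section 6.3 provides for recovery of missing data. Section 11 estimates 24 and 25 patients at two centres and adds a third hospital, so replacement looks feasible. None of this is a stated allowance. The calculation counts patients or units, a unit may have one parent, adults in one household are likely to be correlated, and no replacement rule is given.

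Section 6.3 also says: "A mixed-effects analysis (linear link GLM) will be performed for continuous variables". Such a model can use partial data, but an adult with only a baseline visit adds almost nothing to the estimate of 12-month change.

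A reader might also infer from section 8, Phase 5, that the analysis is restricted to completers. The documents do not support that. The sentence sits in a work plan and reads naturally as timing, since Phase 6 finalises the analysis once all final visits are done. Section 6.3 sets no such restriction, and analysis sets may be defined in a statistical analysis plan that is not at hand.

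**Conclusion.** The point holds as a minor one. On the plain reading, the 80% stated for aMED is not delivered once more than about one pair is lost. Power is then roughly 76 to 78% with 24 complete pairs, 72 to 74% with 22 and 68 to 70% with 20. This rests on a two-sided paired t-test, one pair per unit, no allowance already inside 26, and assumed loss rates.

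A reader might go further and infer that 26 is wrong or that the study is underpowered. Neither can be shown: 26 is right for an SD of change of 1.71 to 1.75 with no loss, and for a smaller SD it leaves room for loss. aHEI power is not at risk, and nothing here indicates bias in any direction.

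**What to change.** Change section 6.4 only. Restate aMED power at the expected number of complete 12-month pairs, for example as a table for 20 to 26 pairs, and give the SD of within-person change, the sidedness and the assumed loss behind it. Suggested wording, with values for the sponsor to fill in:

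*The 26 units [do / do not] include an allowance for loss. The calculation assumes a [one-/two-]sided 5% paired t-test and an SD of within-person aMED change of [value]. With an expected loss of [x]%, about [n] complete 12-month pairs give [y]% power for a 1-point change; power for 20 to 26 pairs is tabulated.*

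If 26 already includes loss, the text should say so and give the net number.

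The cost is one recalculation, a few sentences and possibly a stated power slightly below 80%. No extra enrolment is required. If the sponsor chose to keep 80% and 26 contains no allowance, 26/(1 − loss) gives 28, 29, 31 or 33 units for 5, 10, 15 or 20% loss. The main analysis in section 6.3 is unaffected.

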### 4.2 Primary objective:

- To evaluate changes in dietary patterns and lifestyle among adults living in the family unit of a newly diagnosed patient with T1D one year after the diabetes diagnosis.

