### 4.3 Secondary objectives:

\*Due to the timeliness of the study, we also proposed:

- To characterize changes in the dietary patterns of parents or guardians of patients with T1D during follow-up (6 months after diagnosis).
- To determine, using a questionnaire, changes in the physical activity of the adult subjects in the study at 6 and 12 months.
- To determine, using a questionnaire, the emotional stress produced by the diagnosis and treatment of T1D in the adult parents or guardians belonging to the families of the incident case at 6 and 12 months.
- To determine, using a questionnaire, the level of anxiety and depression produced by the diagnosis and treatment of T1D in the adults in the families at 6 and 12 months.

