### 5.7.1 Main Variables

Eating patterns and dietary information collected using the following questionnaires:

- Semi-quantitative food frequency questionnaire (FFQ) validated in the Spanish population (20). This questionnaire consists of 137 items. They collect the average food intake over the past year. Food consumption frequencies are recorded in nine levels (never or mostly never, 1-3 times/month, 1 time/week, 2-4 times/week, 5-6 times/week, 1 time/day, 2-3 times/day, 4-6 times/day, and more than 6 times/day). Food consumption frequencies will be calculated as the number of meals per day and multiplied by the weight of the portion sizes indicated in the questionnaire. Nutrient intake will be adjusted for energy intake. In addition, participants who have not made any changes to their dietary habits during the past year prior to the study will be asked at the first visit. Nutritional data will be extracted using the Spanish Food Composition Database (BEDCA), developed by the RedBEDCA and the Spanish Agency for Food Safety and Nutrition (21).  
(An English version is attached at the end of this protocol).
- Mediterranean Diet Adherence Index (aMED) to assess the degree of adherence to the Mediterranean Diet. Based on the Mediterranean Diet Scale (22), which includes the intake of vegetables, legumes, fruits, nuts, grains, red and processed meats, fish, the ratio of monounsaturated/saturated fats, and alcohol; the scoring scale ranges from 0 to 9 points.
- Healthy Eating Index (aHEI), based on the American Dietary Guidelines and the Healthy Eating Pyramid (23), which contains 9 items related to healthy food intake, with a maximum score of 87.5.
- Mediterranean Diet Adherence Screener (MEDAS): The MEDAS (Mediterranean Diet Adherence Screener) is a tool used to assess the degree of adherence to the Mediterranean Diet. It consists of 14 questions that explore different aspects of the characteristic dietary pattern of this diet (24). Each question is assigned a value depending on the frequency or quantity of consumption reported. The total score of the MEDAS questionnaire can range from 0 to 14 points, where a higher score indicates greater adherence to the Mediterranean Diet. This questionnaire provides an overview of an individual's dietary pattern and its alignment with the principles of the Mediterranean diet.

Physical Activity Log:

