## **12. PROTOCOL MODIFICATIONS:**

Any modification to the study protocol will always take the form of a written amendment or addendum. Formalization requires the approval of all persons responsible for the study. For significant modifications, express approval from the Clinical Research Ethics Committee will be requested.

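### No primary outcome is named, and the 16-unit contingency in section 6.4 reaches 80% power only on a different diet index (aHEI) from the one that set the sample size (aMED)

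*Protocol*

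**What the plan says.** Protocol section 4.2 gives the primary objective as: "To evaluate changes in dietary patterns and lifestyle among adults living in the family unit", one year after the child's diagnosis. It names no instrument or score. The principal aim in section 1 (Resume) is worded differently. It covers dietary patterns and adds a further target: "to evaluate their evolution and the effect on health indicators after one year of evolution".

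Section 5.7.1, headed Main Variables, opens with "Eating patterns and dietary information collected using the following questionnaires" and lists the FFQ, aMED, aHEI and MEDAS. Under the same heading it goes on to IPAQ, PIP and HADS. Nothing is ranked. Section 4.3, however, places physical activity ("To determine, using a questionnaire, changes in the physical activity of the adult subjects in the study at 6 and 12 months"), parental stress, and anxiety and depression among the secondary objectives.

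Section 6.3 describes a main analysis of changes without naming a variable, and for all analyses sets "statistical significance when p values are less than 0.05".

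Section 6.4 derives 26 family units from 80% power and 5% alpha in a paired pre-post comparison, "to detect a minimum difference of 1 point on the aMED". It then offers a contingency: "recruiting 16 family units would also guarantee a statistical power of 80% and an alpha error of 5"%, this time for 5 points on aHEI. No SD is printed for either index.

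**The concern.** The hypothesis in section 4.1 is that nutritional therapy for the child significantly affects the eating habits and lifestyle of the household. With no primary outcome fixed, a reader cannot tell in advance which result would confirm or refute it. Three overlapping summary scores (aMED, aHEI, MEDAS) are each eligible at the 5% level, so the choice could be made after the results are seen.

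The contingency adds to this. If recruitment falls short, section 6.4 still supplies an 80% power figure, but not for the score that set the sample size. The protocol does not say that aHEI would then take over from aMED, and it does not rule that out. A reader could also take the word *also* to mean that the study stays adequately powered with 10 fewer families (10/26 = 38% fewer). For aMED that cannot be so: if 26 units are needed for 80% power, 16 give less.

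**Working it through.** **Inputs (section 6.4).** Power 80%; alpha 5%, sidedness not stated; paired comparison of means; N = 26 for 1 point on aMED; N = 16 for 5 points on aHEI. No SD of the change and no pre-post correlation is given.

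**Can the plan's figures be reproduced?** Not directly, because the SD is missing. Each N can only be solved backwards for the SD of the change it implies. Since 26 may have been rounded up, N = 25 and N = 26 bracket the answer.

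**Step 1: implied SD of the aMED change.** For the two-sided normal approximation, SD = δ√N / (z₀.₉₇₅ + z₀.₈₀):
- N = 26: 1 × 5.099 / (1.960 + 0.842) = 1.82
- N = 25: 1 × 5.000 / 2.802 = 1.78

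The paired t-test (noncentral t, N − 1 degrees of freedom) gives 1.75 and 1.71.

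**Step 2: power for 1 aMED point at 16 units, SD held fixed.** For the normal approximation from N = 26: Φ(1 × √16 / 1.82 − 1.960) = Φ(2.198 − 1.960) = Φ(0.238) = 59%.

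**Step 3: difference detectable with 80% power at 16 units.** For the normal approximation: 1 × √(26/16) = 1.27 points from N = 26, and √(25/16) = 1.25 from N = 25.

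| Method | Implied SD | Power, n = 16, 1 point | 80%-detectable difference, n = 16 |
|---|---|---|---|
| Paired t, two-sided | 1.71–1.75 | 57.1–58.9% | 1.28–1.31 |
| Normal, two-sided | 1.78–1.82 | 59.4–61.1% | 1.25–1.27 |
| Paired t, one-sided | 1.95–1.99 | 60.6–62.1% | 1.27–1.30 |
| Normal, one-sided | 2.01–2.05 | 62.0–63.5% | 1.25–1.27 |

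**Step 4: why aHEI needs fewer units.** By the two-sided paired t-test, N = 16 for 5 points implies an aHEI SD of 6.43–6.67, a standardised effect of 5/6.67 = 0.75 to 5/6.43 = 0.78. For aMED it is 1/1.75 = 0.57 to 1/1.71 = 0.58. The smaller N comes from a larger standardised target on another scale.

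**Step 5: false positives with three unranked diet scores, each at two-sided 5%.** If independent: 1 − 0.95³ = 14.3%. Simulated paired t-tests with no true change (n = 26, 40,000 runs, equal correlations assumed) give about 14% at correlation 0, 12.5% at 0.5 and 11% at 0.7. At n = 16 the results are much the same.

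**The case against.** The strongest reply is that section 6.4 is open about the contingency. The same sentence goes on to name aHEI and 5 points, and nowhere does it claim that 16 units preserve power for aMED. aMED alone produces the 26 units that the Resume and section 5.1 repeat, so it leads by implication. That is fair as far as it goes, but an implied primary outcome binds no one. If aMED does lead, the 16-unit sentence gives no contingency for it.

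Section 5.7.1 has subheadings, and its heading contrasts with the other relevant variables of 5.7.2. So *main* may simply mean the measures that serve any objective. That softens the clash with 4.3. It also means the heading cannot be read as naming the primary outcome, and the word lifestyle in 4.2 and health indicators in the Resume remain unexplained.

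A shortfall to 16 may be unlikely. Section 11 estimates 24 and 25 patients at two centres and adds a third centre. Consent rates are unknown, however, and the protocol itself plans for 16.

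The power figures are conditional on the back-solved SD. With an SD of change of 1.5 or 2.0, two-sided power at 16 units would be about 70% or 47%. Under a two-sided test, though, those SDs give 90% and 69% power at 26 units, so they do not fit the stated design. An SD near 2.0 fits only a one-sided calculation, which is already in the table.

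Finally, no rule says that one significant score confirms the hypothesis, and zero correlation is implausible when aMED and MEDAS both score Mediterranean diet adherence. The 11–14% is therefore an illustration, and its lower end is the more realistic. A separate analysis plan might handle multiplicity in detail, but naming the primary outcome and matching the sample size to it belong in the protocol.

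**Conclusion.** The concern holds. No section designates a primary outcome, and the 80% power quoted for 16 units belongs to aHEI, not to the index on which the study was sized. On aMED, 16 units give about 57–59% power for 1 point with a two-sided paired t-test (57–63% over all variants), or 80% power for a difference of 1.25–1.31 points. Leaving three diet scores eligible at 5% each would raise the chance of a false claim to about 11–14%.

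These sizes assume that 26 was solved for 80% power with no added allowance, and that the three scores have equal correlations between 0 and 0.7. The missing SDs mean that neither 26 nor 16 can be called wrong. That power on aMED falls below 80% at 16 units needs no SD, provided 26 is the number required. This should be corrected; it does not invalidate the design.

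**What to change.** - In section 4.2, name change in aMED from baseline to 12 months as the single primary outcome, whatever the number recruited. It already sets N, and 12 months matches the one-year objective. Bring the principal aim in the Resume into line.
- In section 5.7.1, label aHEI, MEDAS, FFQ nutrients, IPAQ, PIP and HADS as secondary, consistent with section 4.3.
- In section 6.4, say that the 16-unit figure concerns aHEI only, as a secondary outcome. Add the aMED power or detectable difference at 16 units, computed from the sponsor's own SD, and print that SD.
- Make the change before outcome data are analysed.

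The cost is a written amendment under section 12, which also provides: "For significant modifications, express approval from the Clinical Research Ethics Committee will be requested". Fewer results could be called confirmatory. No additional data or participants are needed.
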